#### 5.11 Adverse event and Serious Adverse Events Reporting and Management

#### Definitions

An adverse event (AE) is any untoward medical occurrence associated with the use of a drug in humans, whether or not considered drug related. Adverse events occur after enrolment and are defined as not being present prior to enrolment.

Serious adverse events (SAEs) are a subset of adverse events that are life threatening, require a surgical or medical procedure to prevent disability or death, result in admission to hospital, prolongation of hospitalization or transfer to an ICU, or results in death. A SAE can also be an important medical event that may not result in death, be life-threatening, or require hospitalization, but may jeopardize the subject and may require medical or surgical intervention to prevent one of the outcomes listed in this definition. A SAE is also an event that results in a congenital anomaly or birth defect.

The pharmacology and risks of alteplase in patients with acute ischemic stroke are well known; in addition, there are multiple recent phase II and one recent phase III trial attesting to the safety of intravenous tenecteplase in patients with acute ischemic stroke. Of note, in particular is the Norwegian Tenecteplase Stroke Trial (NOR-TEST) trial. This Phase III trial randomized 1100 patients using standard thrombolysis eligibility criteria to test if intravenous tenecteplase (at a dose of 0.4 mg/kg body weight) was superior to standard dose alteplase. The dose of intravenous tenecteplase

used in the NORTEST trial was higher than that proposed in this trial (0.25 mg/kg body weight, maximum dose 25 mg) while the dose of intravenous alteplase was the same as in this trial. The table below lists SAEs noted in the NORTEST trial in patients administered intravenous alteplase or intravenous tenecteplase. There was no difference in incidence of SAEs up until day 90 or patients affected by at least one SAE up until day 7. The NORTEST trialists reported the following SAEs, namely, any intracerebral hemorrhage, symptomatic intracerebral hemorrhage, death, angioedema, recurrence of ischemic stroke, epistaxis, chest pain, gastrointestinal bleeding, other extracranial bleeding and readmission as possibly or probably related to drug administration (see Table below). There were no differences in any of these expected SAEs between patients administered intravenous tenecteplase.

Based on data from the NORTEST phase III trial and other recent phase II trials in acute ischemic stroke patients and based on substantial literature attesting to the safety of intravenous tenecteplase in patients with acute myocardial infarction for over 15 years, unexpected serious adverse drug reactions or events are unlikely in the trial. (See Table below for a list of SAEs from the NORTEST trial and Appendix, Table 1 for a list of expected adverse drug reactions that have been well described associated with stroke thrombolysis). The natural history of acute stroke is such that high morbidity is expected (See Appendix Table 1). Since both thrombolytic agents have a biological half-life measured in hours, treatment-related morbidity and AEs will occur within a short interval after administration.

	Tenecteplase (n=549)	Alteplase (n=551)	p value
All SAEs to day 90	145 (26%)	141 (26%)	0.74
Patients with at least one SAE up to day 90	127 (23%)	120 (22%)	0.59
Patients with at least one SAE up to day 7	61 (11%)	56 (10%)	0-62*
Possibly or probably related to study drug	51 (9%)	53 (10%)	0.85*
Any ICH†	47 (9%)	50 (9%)	0-82*
Symptomatic ICH‡	15 (3%)	13 (2%)	0.70*
Death	15 (3%)	14 (3%)	0.84*
Angio-oedema	1(<1%)	2 (<1%)	1.00*
Recurrence of ischaemic stroke	9 (2%)	5 (<1%)	0-30*
Recurrence of transient ischaemic attack	1(<1%)	0	0-50*
Epistaxis	0	1(<1%)	1-0*
Chest pain	3 (<1%)	5 (<1%)	0.73*
Gastrointestinal bleeding	1 (<1%)	o	0-50*
Other extracranial bleeding	4 (<1%)	9 (2%)	0.26*
Readmission	14 (3%)	22 (4%)	0-24*
Patients with at least one SAE, days 8–90	74 (13%)	75 (14%)	0-95
Possibly or probably drug related	6 (1%)	8 (1%)	0.79*
ICHS	6 (1%)	7 (1%)	0.79*
Death	14 (3%)	12 (2%)	0-68*
Angio-oedema	0	0	NA
Recurrence of ischaemic stroke	4 (<1%)	6 (1%)	0.75*
Recurrence of transient ischaemic attack	4 (<1%)	1 (<1%)	0-21*
Epistaxis	0	0	NA
Chest pain	4 (<1%)	7 (1%)	0-55*
Gastrointestinal bleeding	2 (<1%)	0	0.25*
Other extracranial bleeding	1 (<1%)	4 (<1%)	0-37*
Readmission	63 (11%)	68 (12%)	0.71

# Table above shows a list of SAEs in the intravenous tenecteplase vs. intravenous alteplase arms of the NORTEST trial.

Investigators are directed to the following product monographs for expected adverse drug reactions of alteplase and tenecteplase.

1. Alteplase (Activase)

http://www.rochecanada.com/content/dam/roche\_canada/en\_CA/documents/Research/C linicalTrialsForms/Products/ConsumerInformation/MonographsandPublicAdvisories/Ac tivase/Activase\_AIS\_PM\_E.pdf

2. Tenecteplase (TNKaseTM)

http://www.rochecanada.com/content/dam/roche\_canada/en\_CA/documents/Research/C linicalTrialsForms/Products/ConsumerInformation/MonographsandPublicAdvisories/T NKase/TNKase\_PM\_E.pdf

The trial intends to obtain AE and SAE data through a combination of a) the study database b) the ongoing QuICR and OPTIMISE registries and c) through linkages to administrative data sources. The following AEs/SAEs that occur during hospital stay are captured in the QuICR\* and OPTIMISE# registries.

- Urinary tract infection\*
- Pneumonia\*
- Deep venous thrombosis\*
- External ventricular drain placement\*
- Recurrent stroke\*
- Hemicraniectomy\*
- Sub-occipital craniectomy\*
- Symptomatic intracerebral hemorrhage\*#
- Intracerebral Hemorrhage\*
- Groin or arterial access site hematoma#
- Endovascular procedure-related vessel perforation#
- Endovascular procedure-related vessel dissection#

\*Indicates data collected in the QuICR registry # Indicates data collected in OPTIMISE registry

Table 1 in the Appendix represents an empiric last of AEs and SAEs derived from the pooled database of multiple clinical trials. These are published, known adverse events associated with stroke because these are control arm patients only. The combined list above and the list in the Appendix will all be considered EXPECTED adverse events for the trial.

The following steps will be used to collect data on the above adverse events:

- Given the short half-life of both thrombolytic agents (tenecteplase and alteplase) and known safety profile, adverse events occurring within the first 24 hours attributable (related) to either agent that correspond to known effects of these drugs or of hyperacute stroke (Appendix, Table 1) will be considered expected. Adverse events that occur beyond 24 hours will be considered unrelated to study drug.
- 2. Data on SAEs occurring within the first 24 hours including SAEs of special interest for the study, namely, a) symptomatic intracerebral hemorrhage (post-acute stroke treatment defined as per QuICR and OPTIMISE registries) b) angioedema and c) peripheral bleeding requiring blood transfusion will be collected through the trial database.
- 3. AEs measured routinely by the QuICR and OPTIMISE registries (highlighted as \* or # above) will be collected from those registries.
- 4. Administrative data linkages will be used to collect data on other AEs. The Canadian Discharge Abstract Database (DAD) captures all hospital separations for all Canadian provinces and

territories, with the exception of the province of Quebec. Each hospital discharge record includes up to 25 diagnosis codes, recorded using the ICD coding system, along with other clinical and demographic information. In addition, each diagnosis field in the database has an accompanying single digit field for the diagnosis type that is recorded whenever a diagnosis is recorded. The diagnosis type codes are as follows: type M: most responsible diagnosis; type 1: preexisting conditions (comorbidities) that influence care, or the hospital stay; type 2: conditions that arose after admission and that may thus represent complications of care; and type 3: preexisting conditions (comorbidities) that do not influence care, or the hospital stay. Type 2 diagnosis type codes will be used primarily to identify any AEs. Other data elements as relevant (interventions offered during admission; Group 11 or Blood transfusion given; Group 17) will also be collected. It will therefore not be possible to classify seriousness when data are obtained through administrative data linkages. Details on the data elements collected through DAD in each province will be made available in the MOP. The nature of the specific data linkages will be different in different jurisdictions (Alberta vs. Ontario). Data will be queried and obtained at regular intervals through the duration of the trial from the above data sources.

5. Although we predict that there will be no adverse events that will be classified as serious, unexpected and related, we will maintain constant contact with investigators to manage this rare possibility. Investigators are under obligation under the *Protecting Canadians from Unsafe Drugs Act (Vanessa's Law)* (Canada), to report potential Serious Unexpected Adverse Drug Reactions (SUADR) and we will utilize our relationship with the sites to identify any event that fits this definition.

The Trial Safety Committee will review unblinded safety data throughout the trial to ensure that events are being reported and they fall within accepted norms for routine stroke care. The DSMC will periodically review unblinded overall safety data to determine patterns and trends of events, or to identify safety issues, which would not be apparent on an individual case basis. Details of the DSMC review are outlined in the DSMC Charter. Management of AEs will be as per local jurisdictions.

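### Section 5.11 lets a list of control-arm stroke events decide whether a drug-related serious event is expected, so some such events may not be escalated as unexpected drug reactions

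*Combined protocol and SAP*

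**What the plan says.** All of this is in protocol section 5.11 and the Appendix.

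- **Table 1 as drug reactions.** The text before the table of serious events from the Norwegian phase III trial sends the reader to "Appendix, Table 1 for a list of expected adverse drug reactions that have been well described associated with stroke thrombolysis".
- **Table 1 as disease events.** Further on, the same table is said to come from pooled trial data: "These are published, known adverse events associated with stroke because these are control arm patients only".
- **Drug reference.** "Investigators are directed to the following product monographs for expected adverse drug reactions of alteplase and tenecteplase".
- **General declaration.** "The combined list above and the list in the Appendix will all be considered EXPECTED adverse events for the trial". The list above is most naturally the 12 registry-captured items, which include "Endovascular procedure-related vessel perforation".
- **Step 1 of the collection procedure.** Events in the first 24 hours attributed to either agent "that correspond to known effects of these drugs or of hyperacute stroke (Appendix, Table 1) will be considered expected". It continues: "Adverse events that occur beyond 24 hours will be considered unrelated to study drug".
- **Step 2.** Serious events in the first 24 hours go into the trial database. Symptomatic intracerebral haemorrhage, angioedema and bleeding that needs transfusion are named as being of special interest.
- **Step 5 and the closing paragraph.** "Although we predict that there will be no adverse events that will be classified as serious, unexpected and related", investigators keep their statutory duty to report potential serious unexpected adverse drug reactions (SUADRs). The Trial Safety Committee and the DSMC both review unblinded safety data.

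**The concern.** Expectedness of a drug reaction asks whether the event, once attributed to the drug, is already described for that drug. A list of what happens to stroke patients in control arms answers a different question: what the disease does. Such a list helps in judging causality. It cannot show that a reaction is already known for the drug.

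Section 5.11 merges the two questions at the point where it matters, after relatedness has been judged. Escalation of a single case depends on the event being serious, related and unexpected together. If the disease list settles the third element, a new kind of serious reaction can drop out of that class because stroke patients also have such events. The issue bears most on tenecteplase, which is labelled investigational in this trial (section 5.2.1.1) and for which section 4.4 acknowledges less experience in ischaemic stroke.

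**Working it through.** The protocol gives no figure to reproduce. The check is a reading of the rules plus a count of Appendix Table 1.

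**1. Is Table 1 operative for related events?** Yes. Step 1 is limited to events in the first 24 hours already attributed to a study drug, and gives two alternative routes to expected:

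- Route A: a known effect of these drugs.
- Route B: a known effect of hyperacute stroke, with Table 1 as the reference.

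Either is enough. The general declaration points the same way and has no exception for related events.

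**2. What remains in the escalation class?** An event must be serious, within 24 hours (later events are deemed unrelated), not a known effect of either drug, and not on Table 1 or the registry list. Without Route B and the general declaration, the last condition disappears. The affected group is therefore related serious events within 24 hours that match a listed term but are not a known effect of the drug received.

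**3. How broad is the list?** The serious-event column of Table 1 has 68 terms. They include shock, cardiogenic shock, respiratory arrest, cardiac arrest, multi-organ failure and renal failure, non-specific labels under which an unrecognised reaction could be coded.

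Some terms match risks that section 4.4 gives for both drugs (intracranial and other bleeding, transient hypotension) and would be expected through Route A:

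- Bleeding: cerebral hemorrhage, hemorrhagic transformation, hemorrhagic cerebral infarction, gastrointestinal hemorrhage, rectal hemorrhage, hematuria, melena = 7.
- Hypotension = 1.

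68 − (7 + 1) = 60 terms do not match section 4.4 on their face. This is a ceiling. Other terms may be in the monographs, or may match events that the Norwegian trial reported as possibly or probably drug-related, such as recurrent ischaemic stroke.

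**4. Are the two descriptions of Table 1 compatible?** No. One calls it expected drug reactions of stroke thrombolysis. The other calls it stroke events, on the ground that the patients are control-arm only. The second undercuts using the table as drug reference information.

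**5. Could Table 1 serve as background rates instead?** Not as printed. The serious-event figures rise at every row, from 11.2 to 79.4 per 1,000. Melena is 79.1 as a serious event against 3.98 as an adverse event; nausea is 79.4 against 68.92. Section 5.11 defines serious events as a subset of adverse events, so these cannot be incidences of single terms. The column appears to be cumulative.

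**The case against.** The strongest case on the other side is that the protocol has several safeguards. Step 2 collects serious events in the first 24 hours whether expected or not. Step 5 keeps the duty to report potential SUADRs and promises constant contact with investigators. Two bodies see unblinded data. No sentence tells sites to code expectedness or bars escalation. Many listed terms are legitimately expected, and the monograph content is not available here.

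Much of this stands, and it limits the point. It does not remove it. Collection is not escalation of a single case. The reporting duty turns on the word unexpected, which section 5.11 defines. The DSMC is asked to look for patterns not visible case by case, and the Trial Safety Committee to check against norms for routine stroke care. Neither is described as re-judging expectedness.

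A reader might infer more than the documents support:

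- **That drug-caused serious events would never be reported.** Events on neither list that are not known drug effects can still be SUADRs, and the safeguards above apply to the rest.
- **That the expected set comes only from untreated patients.** The text says control-arm, not untreated. The set also takes in the registry items and known drug effects, and the section calls the Norwegian trial's drug-related events expected.
- **That angioedema falls between the lists.** It is on neither, but section 4.4 describes it after both drugs and section 5.11 counts it among the expected events of the Norwegian trial, so Route A covers it.
- **That the SAP's row for other SAEs and SUSARs (section 9) would be near zero.** An expected serious event is still a serious event. Only the SUSAR part could shrink, and mortality, symptomatic haemorrhage, angioedema and transfusion-requiring bleeding have their own rows.

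**Conclusion.** The point holds as a defect in the expectedness rule. Section 5.11 lets a natural-history list override the drug reference for events already judged related, and it contradicts itself on what that list is. The consequence is that some related serious events within 24 hours may be classed as expected and not escalated individually. They are not lost from the trial data.

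The size is bounded only loosely. The serious-event list has 68 terms, of which at most 60 are not obviously covered by the risks in section 4.4. The number outside the monographs, and the number of patients affected, cannot be derived from the documents. The conclusion assumes that those who assess cases follow step 1 as written and that the DSMC charter and manual of procedures, which are not available here, do not set a different rule.

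The adjacent 24-hour rule narrows the class further. It also sits uneasily with the protocol's own table from the Norwegian trial, where days 8–90 show 6 tenecteplase and 8 alteplase patients with serious events possibly or probably drug-related.

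The prediction of no serious, unexpected and related events therefore follows partly from the definitions and should not be read as independent reassurance. The amendment should be made; the design, endpoints and sample size are unaffected.

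**What to change.** Amend section 5.11 in three places.

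1. **Step 1.** Remove hyperacute stroke and Appendix Table 1 as a route to expectedness for related events. Judge a related serious event against the reference information for the drug the patient received, using the monographs already cited.
2. **General declaration.** Reword it so that Table 1 and the registry list are anticipated disease- or procedure-related events which do not decide whether a drug-related serious event is unexpected.
3. **Description of Table 1.** Correct the earlier sentence so that it describes events in control-arm stroke patients, in line with the later one.

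Do not offer Table 1 to the DSMC as background rates, because its serious-event column appears to be cumulative.

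The cost is a wording amendment and a note to sites. The downside is possibly a few more expedited reports; the documents do not allow an estimate of how many.

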## APPENDIX

Table 1: List of Adverse Events. (Stroke. 2014; 45: 2677-2682)

Adverse Event (AE)	Incidence	Serious Adverse Event	Incidence
	(AEs/	(SAE)	(AEs/

		QUICR & OPTIMIST	
	1,000		1,000
	patients)		patients)
Pyrexia	160.69	Stroke in Evolution	11.2
Headache	137.32	Pneumonia	16.8
Urinary Tract Infection	87.45	Ischemic Cerebral Infarction	21.7
Anxiety	90.04	Brain Edema	26.0
Constipation	88.48	Cardiac Failure	29.4
Hypertension	75.67	Myocardial Infarction	32.3
Pneumonia	65.63	Cerebral Hemorrhage	34.8
Nausea	68.92	Aspiration Pneumonia	37.3
Vomiting	67.88	Respiratory Failure	39.5
Stroke in Evolution	60.95	Hemorrhagic Transformation	41.7
Hypokalemia	57.32	Pulmonary Embolism	43.7
Atrial Fibrillation	52.81	Atrial Fibrillation	45.5
Depression	44.16	Urinary Tract Infection	47.2
Somnolence	32.38	Pulmonary Edema	48.7
Insomnia	39.31	Cerebrovascular Disorder	50.2
Cardiac Failure	33.94	Cardiac Arrest	51.7
Hypotension	36.36	Carotid Artery Disease	53.1
Hematuria	35.15	Sepsis	54.3
Brain Edema	30.13	Angina Pectoris	55.5
Pain	25.97	Hypotension	56.6
Hemorrhagic	28.92	Coma	57.7
Transformation			
Edema Peripheral	25.80	Pyrexia	58.8
Bradycardia	30.48	Renal Failure	59.8
Ecchymosis	25.97	Headache	60.7
Diarrhea	29.61	ICP increased	61.6
Ischemic Cerebral	28.57	Respiratory Tract Infection	62.5
Infarction		1 5	
Cerebral Hemorrhage	24.59	Bradycardia	63.3
Angina Pectoris	26.32	Transient Ischemic Attack	64.1
Aspiration Pneumonia	24.76	Gastrointestinal Hemorrhage	64.9
Cough	23.72	Hypertension	65.6
Dyspnea	24.94	Hemorrhagic Cerebral	66.3
5 1		Infarction	
Hyperglycemia	24.76	Somnolence	67.1
Tachycardia	24.24	Cerebral Incarceration	67.6
Musculoskeletal Pain	23.72	Deep Vein Thrombosis	68.2
Back Pain	24.07	Syncope	68.8
Confusional State	20.61	Depression	69.3
Respiratory Tract Infection	19.05	Hematuria	69.7
Rash	18.18	Vomiting	70.2
Purpura	11.77	Cerebrovascular Accident	70.6

		QUICR & OPTIM	AISE
Pulmonary Edema	17.66	Convulsion	71.0
Urinary Incontinence	13.16	COPD	71.4
Myocardial Infarction	16.80	Dyspnea	71.8
Respiratory Failure	15.24	Anemia	72.2
Anemia	14.72	Aspiration	72.5
Abdominal Tenderness	17.49	Bronchitis Acute	72.9
Rhonchi	12.64	Cardiopulmonary Failure	73.2
Lung Crepitation	12.47	Constipation	73.6
Extrasystoles	13.16	Epilepsy	73.9
Restlessness	16.10	Abdominal Tenderness	74.2
Bronchitis Acute	14.89	Dehydration	74.6
Pulmonary Congestion	11.77	Ileus	74.9
Urinary Retention	13.51	Septic Shock	75.2
Renal Failure	12.29	Colon Neoplasm	75.5
Conjunctivitis	11.43	Rectal Hemorrhage	75.8

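### Protocol 5.11 declares every adverse event after 24 hours unrelated to study drug, contradicting the phase III table in the same section and making late drug-related SAEs zero by definition

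*Combined protocol and SAP*

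**What the plan says.** Protocol 5.11 sets relatedness by time since treatment: "Adverse events that occur beyond 24 hours will be considered unrelated to study drug". The reason given is the short half-life of both drugs, so that "treatment-related morbidity and AEs will occur within a short interval after administration".

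The same section reproduces the SAE table of the earlier phase III trial. Under "Patients with at least one SAE, days 8–90" it has a row "Possibly or probably drug related", with 6 patients on tenecteplase and 8 on alteplase.

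On collection, the trial database takes "Data on SAEs occurring within the first 24 hours including SAEs of special interest for the study" (symptomatic intracerebral hemorrhage, angioedema and transfused peripheral bleeding). Protocol 5.3 and 7.2 repeat the 24-hour limit. Later events come from the two registries during the hospital stay, or from administrative discharge data. Protocol 5.11 says the discharge data cannot be graded for seriousness and do not cover Quebec.

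Item 5 of the collection steps in 5.11 reminds investigators of their legal duty to report potential serious unexpected adverse drug reactions (SUADRs) and gives no time limit. SAP section 9 compares other SAEs and SUSARs by arm and gives no time window.

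**The concern.** The protocol cites the phase III table as evidence of safety, yet its own rule would overrule that table's causality judgments. Item 5 of 5.11 describes the reportable class as events that are serious, unexpected and related. If relatedness is ruled out after 24 hours, that class is empty from then on whatever happens to patients. A zero count of late reactions would then reflect the definition and carry no information about the drugs. Sites would also hold two instructions that cannot both be followed for a suspected late reaction.

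A second matter is how far late SAEs are captured at all. The SAP rows carry no time window, so a table drawn mainly from the first 24 hours could be read as covering full follow-up.

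**Working it through.** **1. The table's late related SAEs.** Inputs from the table in Protocol 5.11: 549 tenecteplase and 551 alteplase patients; related SAEs on days 8–90 in 6 and 8.

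- Reproduction: 6/549 = 1.09% and 8/551 = 1.45%; two-sided Fisher exact p = 0.789. The table prints 1%, 1% and 0.79, so it is reproduced.
- Under the 24-hour rule: 6 + 8 = 14 related becomes 0.
- Pooled rate: 14/1100 = 1.27%. Exact (Clopper–Pearson) 95% CI: lower = Beta quantile 0.025 with parameters (14, 1087) = 0.70%; upper = Beta quantile 0.975 with parameters (15, 1086) = 2.13%.
- Scaled to this trial, assuming the rate carries over: 1600 × 1.27% ≈ 20 patients; range 1600 × 0.70% ≈ 11 to 1600 × 2.13% ≈ 34.
- Dose check: 5.11 says the cited trial used a different tenecteplase dose but the same alteplase dose. The alteplase arm alone gives 800 × 8/551 ≈ 12 patients per arm of 800.
- The table also shows 51 and 53 patients with related SAEs up to day 7. That row includes the first 24 hours and is not split there, so it is not evidence about timing beyond 24 hours. Fourteen is therefore a minimum for the cited trial.

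**2. What depends on attribution.**

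| Item | Location | Uses relatedness? |
|---|---|---|
| Death within 90 days | Protocol 5.9 | No |
| Mortality stopping guidance | Protocol 6.7, SAP 6 | No |
| DSMC review of overall safety data by arm | Protocol 5.11 | No |
| Mortality, symptomatic ICH, ICH on imaging, transfused bleeding, angioedema, other SAEs | SAP 9 | No |
| SUSARs | SAP 9 | Yes |
| SUADR reporting | Protocol 5.11, item 5 | Yes |

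Only the last two are emptied by the rule.

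**3. What is captured after 24 hours.** Symptomatic ICH during the hospital stay is marked as a field of both registries in 5.11. Intracerebral hemorrhage of any kind is marked for QuICR only. Angioedema and serious extracranial bleeding are in neither list; the nearest field is access-site hematoma, in OPTIMISE only. For other late events the source is administrative data without a seriousness grade.

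**4. Appendix Table 1.** The SAE column is headed as incidence per 1,000 patients.

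- Its 68 values rise without exception from 11.2 to 79.4 and sum to about 4,226 per 1,000, or more than four SAEs per patient.
- 5.11 defines SAEs as a subset of AEs, yet 41 of 52 terms found in both columns have a higher SAE than AE figure. Gastrointestinal hemorrhage is 64.9 as SAE against 6.23 as AE.
- Successive differences give 64.9 − 64.1 = 0.8 for gastrointestinal hemorrhage, 34.8 − 32.3 = 2.5 for cerebral hemorrhage and 32.3 − 29.4 = 2.9 for myocardial infarction. After differencing, 0 of 52 terms exceed the AE figure.

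The column is a running total.

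**The case against.** The strongest reply is that relatedness is only a label. In an open-label trial, causality judged by people who know the allocation can differ between arms, whereas comparisons by randomized arm need no such judgment. The planned comparisons and the stopping guidance are of that kind. This stands, and it limits the point: a reader might infer that late harm would go uncounted because of the 24-hour sentence, and the documents do not support that.

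Second, many bleeds would escape the SUADR route even without the rule. Expectedness in 5.11 depends on being listed, and cerebral hemorrhage, gastrointestinal hemorrhage, melena, hematuria and epistaxis are in Appendix Table 1. This also stands. Deleting the sentence would not turn listed bleeds into unexpected reactions; what it restores is the possibility of classifying any late event as related.

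Third, the half-life argument may be right and the cited trial's late judgments wrong. The documents cannot settle that. But the half-life passage claims a short interval without deriving 24 hours from it, and the protocol cannot both rely on the table and contradict it without comment. The different tenecteplase dose does not resolve this, since 8 of the 14 patients were on alteplase.

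Fourth, a reader might infer that the inflated Appendix column would hide an excess of harm, because the Trial Safety Committee reviews data "to ensure that events are being reported and they fall within accepted norms for routine stroke care". The documents do not name Table 1 as that norm. It is used as a list of expected events, and no analysis, threshold or stopping rule uses its rates. The column is mislabelled; it does not cause under-counting.

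**Conclusion.** The contradiction is real and lies within one section. The rule fixes related SAEs after 24 hours at zero, where the protocol's own table shows at least 14 of 1100 patients (1.27%, 95% CI 0.70% to 2.13%). It also conflicts with the SUADR duty in the same section. The projection of about 20 of 1600 patients (11 to 34) assumes that the cited trial's late rate and its standard of causality apply here.

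The effect is confined to causality classification and the reporting that follows from it. The primary analysis is untouched. Possible under-capture of late non-fatal SAEs is a separate limitation, arising from the 24-hour database entry and ungraded administrative data. Its size cannot be estimated: the SAP gives no window for these rows, and the symptomatic ICH definition sits in the manual of procedures, which is not among the documents. The Appendix column is a labelling error only.

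**What to change.** - Reconcile the half-life statement, the phase III table, the 24-hour rule and the SUADR paragraph in Protocol 5.11: delete automatic unrelatedness and have causality judged for each event. The cost is more late events to assess, by assessors who know the allocation. For that reason, state in the SAP that between-arm safety comparisons do not depend on attribution.
- In SAP 9, give the source and time window of each safety row. Compare symptomatic ICH by arm over the whole hospital stay, using the field both registries already hold. Sites admitted under Protocol 6.5 on administrative data alone would lack that field and need a stated source.
- Label the trial-database SAE, angioedema and transfused-bleeding rows as within 24 hours where that is their only source. Extending them through the registries is not a wording change, because neither registry list includes angioedema or serious extracranial bleeding.
- Minor: head the SAE column of Appendix Table 1 as cumulative, or replace it with per-event incidences. Taking the latter from the source is better than differencing one-decimal figures, whose steps at the end of the column are only 0.2 to 0.3.

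Apart from the extra causality assessments, these are text changes that use data already planned for collection.
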